5.0 STUDY TREATMENT

5.1 *Study Product Formulation and Preparation*

Vitamin D capsules will be supplied as 2000 IU capsules and will be taken as two capsules once daily. Store at 15°-30°C (59°-86°F). Do not expose to excessive heat or moisture.

5.2 Concomitant Medications

All concomitant medications will be recorded on existing CRFs for CCTG 595, with particular attention to vitamin D content of dietary supplements. Use of >400 IU of vitamin D3 in any dietary supplement (such as a multivitamin) will be prohibited.

6.0 CLINICAL AND LABORATORY EVALUATIONS

These will be performed as per the main study. All assays on subjects and controls will be performed on stored samples already being collected by the main study.

The only additional evaluation that will be performed will be calculating the average daily dietary intake of vitamin D and calcium from food. The participants will be asked to recall food items eaten over the last 3 days at the week 36 visit, and the calculator used in the ACTG 5280 study, which is adopted from the USDA database, will be used to quantify vitamin D and calcium intake.

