¹ Pre: attitudes toward safe sex, disclosure, access to care, social support, texting ability, Kalichman sexual compulsivity; Post: satisfaction with iTAB; Pre/Post: HIV literacy, stigma and disclosure, AUDIT, DAST-10 ² includes: risk behavior, adherence assessments, intention to adhere, PHQ9, SCID substance use screen ³ Perform if HIV+ ⁴ Any time history or symptoms suggest potential HIV or STI, check with study MD for appropriate test ⁵ Subjects may have an interim visit if past window of scheduled visit, next visit should be back to regular schedule ⁶ To be performed at week 36 only ⁷ Performed only once on or after Week 48 coinciding with STI screening (Week 48, 72, or 96)											

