6.3.10 T-cell counts and Virology tests

Plasma HIV-1 RNA

An HIV-1 RNA viral load will be performed at the site's local laboratory within 7 days of a new positive antibody test or NAT.

An HIV drug resistance test should be performed with detectable viral load of greater than 500 copies/mL.

CD4 T-cell enumeration will be performed to obtain absolute CD4+/CD8+ count and percentages within 7 days of new HIV diagnosis.

6.3.11 *Stored Plasma and other specimens*

Stored plasma will be collected at day 0, at all visits and with any new HIV diagnosis.

*Specimens will be stored at the site's local laboratory and batched shipped to the central laboratory (UCSD) after completion of the study.

6.3.12 *Pharmacokinetic Studies*

At each visit, record the time and date of the last 3 doses of TDF/FTC medication in the CRF. Dried blood spots will be stored at -80 at each visit beginning at Week 12 for possible future use for plasma and intracellular TFV and FTC pharmacology.

6.3.13 *Questionnaires*

At each visit, the subject should complete the self-reported questionnaires.

6.3.14 *Rectal swabs*

At day 0 and at one additional time point on or after Week 48, all subjects will have a rectal swab stored for possible future studies of the gut microbiome. These tests will be done in retrospect and not available for the subjects.

6.3.15 At day 0, all subjects will have blood stored for future use to examine host DNA. Subjects will sign a consent that informs them of the storage of material for possible host genomic testing.

6.3.16 Participants will be asked to recall food items eaten over the last 3 days at the week 36 visit. The calculator used in the ACTG 5280 study, which is adopted from the USDA database, will be used to quantify vitamin D and calcium intake (see Appendix VI).

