CCTG 595 Vitamin D Sub-study

Effect of Vitamin D Supplementation on Bone Turnover Markers during Tenofovir-Emtricitibine Pre-Exposure Prophylaxis in Men Who have Sex with Men

DESIGN	
CCTG 595 is an open-label clinical trial of the effect of text messaging intervention vs. standard of care on adherence to Truvada (tenofovir-emtricitibine) as PrEP in MSM at increased risk of HIV infection.
 
This sub-study is a matched case-control study, in which cases prospectively take vitamin D3 4000 IU/day beginning at week 24 of PrEP.

DURATION	
Subjects will be followed for 6 months (24 weeks)

SAMPLE SIZE	
50 eligible subjects will receive vitamin D and will be compared to 50 matched control subjects from CCTG 595 who are not participating in this sub-study.

POPULATION	
HIV-negative men aged ≥ 18 years initiating CCTG 595, who are not taking bisphosphonates and do not have a history of osteoporosis, fragility fracture, or kidney stones, or use of tenofovir prior to entry into CCTG 595

REGIMEN	
Vitamin D3 4000 IU/day from week 24 through 48 of PrEP with Truvada

ENDPOINTS	
Primary endpoint will be changes in bone turnover markers from week 24 through week 48 in the vitamin D intervention group as compared to age- and BMI-matched controls

ANALYSIS	
A sample size of 44 subjects per group will provide 80% power to detect a 20% change in P1NP means from week 24 through week 48 between matched cases and controls using a paired t-test with a two-sided $\alpha = 0.05$. To account for attrition, a sample size of 100 is proposed, including 50 vitamin D treated cases and 50 matched controls from CCTG 595.

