9.2 Analyses

All analyses are ITT, unless specified otherwise. Evaluable subjects will be individuals who agree to participate in the vitamin D substudy. The primary endpoint analysis will use a paired t-test to compare the changes in P1NP levels from week 24 to 48 weeks between cases and matched controls. Secondary endpoint analyses will include comparison of changes in 25-OH vitamin D levels, PTH, and CTX and will be analyzed analogously to the primary endpoint. If parametric assumptions fail, the corresponding non-parametric test will be applied, in this case, the Wilcoxon signed rank test. Sensitivity analyses will include linear regression models that adjust for possible confounding covariates, such as dietary intake.

Matching: Concurrent controls who are not enrolled in the vitamin D substudy who are reporting supplementation with ≤ 400 IU of vitamin D/day will be matched 1:1 by randomization arm in the CCTG 595 main study (text messaging arm vs. standard of care), age (± 5 years), race/ethnicity, season of study entry, and BMI (± 3 kg/m²).

REFERENCES

1. DHHS Panel on Antiretroviral Guidelines for Adults and Adolescents. Guidelines for the use of antiretroviral agents in HIV-1-infected adults and adolescents. 2014; <http://www.aidsinfo.nih.gov/ContentFiles/AdultandAdolescentGL.pdf>. Accessed May 1, 2014.

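### The vitamin D sub-study plans to adjust for diet as a confounder, but measures diet only at week 36, 12 weeks after cases start vitamin D

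*Combined protocol and SAP*

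**What the plan says.** The sub-study synopsis sets the regimen as "Vitamin D3 4000 IU/day from week 24 through 48 of PrEP with Truvada". Treatment is not randomised. Sub-study 9.2 states that "Evaluable subjects will be individuals who agree to participate in the vitamin D substudy", and controls come from main-study participants who are not in the sub-study.

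Three places give the timing of the diet measurement, and they agree. Sub-study 6.0 asks participants to "recall food items eaten over the last 3 days at the week 36 visit". Main protocol 6.3.16 says "Participants will be asked to recall food items eaten over the last 3 days at the week 36 visit", worded for participants in general and so covering controls. Footnote 6 to the schedule in main protocol 6.1 says "To be performed at week 36 only". Sub-study 6.0 also says "The only additional evaluation that will be performed will be calculating the average daily dietary intake of vitamin D and calcium from food", so no other sub-study assessment could supply an earlier diet value.

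On analysis, sub-study 9.2 says "The primary endpoint analysis will use a paired t-test to compare the changes in P1NP levels from week 24 to 48 weeks", comparing cases with matched controls and with no covariates. It then adds: "Sensitivity analyses will include linear regression models that adjust for possible confounding covariates, such as dietary intake". Matching is 1:1 on main-study arm, age, race/ethnicity, season of study entry and BMI, and controls must report no more than 400 IU/day of supplemental vitamin D. Diet is not a matching factor. Intention to treat is the stated default for all sub-study analyses.

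**The concern.** A variable used to adjust for confounding should be measured before exposure begins. This matters most where exposure is chosen rather than randomised and everyone knows who is exposed. Both conditions apply here. A diet value taken halfway through treatment mixes two things: the intake a person would have had anyway, which is the possible confounder, and any change in eating that followed from joining a sub-study about bone health. The plan has no earlier measurement that would separate them.

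Diet is also not a peripheral covariate for this sub-study. It is the only one that 9.2 names for the regression, and matching does not deal with it. The sub-study background omits supplemental calcium because dietary calcium is expected to be adequate. At stake is whether a reader can take the diet-adjusted estimate as a test of confounding. If the adjusted and unadjusted results differ, the plan gives no way to tell whether a real confounder has been removed or part of what followed from joining.

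**Working it through.** **1. Timing.** Vitamin D starts at week 24 and ends at week 48 (sub-study synopsis and 3.0). The recall is at week 36 (sub-study 6.0, main protocol 6.3.16, footnote 6).

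- Time on vitamin D at recall: 36 − 24 = 12 weeks.
- Length of supplementation: 48 − 24 = 24 weeks, so the recall falls at the midpoint.
- Diet measurements planned at or before week 24: none.

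**2. Which analyses use diet.** The primary analysis does not. The sensitivity regression does. Matching does not.

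**3. How far the adjusted estimate could move.** The plan states no figure for this, so there is nothing to reproduce. The inputs are:

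- SD of the change in P1NP: 40% (sub-study 9.1).
- Target difference: 20 points (sub-study synopsis and 9.1).
- Shift in cases' intake caused by joining, τ: 0 to 0.5 SD (assumed).
- Correlation of intake with P1NP change, r: 0.2 to 0.3 in absolute value (assumed).

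Suppose intake moves P1NP change by γ points per SD of intake, with |γ| = r × 40. This gives 8 points at r = 0.2 and 12 points at r = 0.3. If joining shifts cases' intake by τ SD and diet is otherwise balanced, the unadjusted group difference includes γτ and the regression on week-36 diet removes it. The size of the move is therefore |γτ| = τ × r × 40.

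| Shift τ (SD) | r = 0.2 | r = 0.3 |
|---|---|---|
| 0 | 0 | 0 |
| 0.25 | 0.25 × 0.2 × 40 = 2.0 | 0.25 × 0.3 × 40 = 3.0 |
| 0.5 | 0.5 × 0.2 × 40 = 4.0 | 0.5 × 0.3 × 40 = 6.0 |

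The range is 0 to 6 points, or 0 to 30% of the target (6 / 20 = 0.30). The direction depends on the signs of γ and τ, and the documents give neither.

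**4. Missing recalls.** Main protocol 8.1.7 discontinues a subject who misses two consecutive scheduled visits before week 48. One missed visit does not, so week 36 can be missed and week 48 attended. Sub-study 9.2 has no rule for a missing recall. Stopping study medication does not by itself lose the visit, because main protocol 6.4 keeps such subjects on the same schedule.

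**The case against.** The strongest defence is that week 36 was a sensible choice. It is the midpoint of the interval over which the outcome is measured, so it describes intake while the change in P1NP accrues. The hypothesis concerns supplementation, not whatever change in eating accompanies enrolment. On that view a diet change after joining is a co-intervention. Adjusting for week-36 intake would remove it, and a week-24 value would leave it in. Week-36 intake may also stand in for stable habitual diet.

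Part of this stands. If diet did not shift, the week-36 value serves as well as an earlier one, and an analysis that holds on-treatment intake fixed is legitimate if declared. But it answers a different question. Sub-study 9.2 describes the covariates as confounders and makes intention to treat the default, and it nowhere states a co-intervention aim or a stable-diet assumption. Without an earlier value, that assumption cannot be checked.

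Three stronger readings are tempting, and the documents do not support them.

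- *That the regression is the only protection against confounding.* The 1:1 matching on five factors, with the supplement limit on controls, is confounding control. The wording of 9.2 also gives diet as an example and not as a closed list.
- *That the sub-study's limit on vitamin D supplements pushes cases' measured intake away from controls'.* Sub-study 4.2.3 already excludes users of more than 400 IU/day, controls are selected at the same threshold, and the recall covers food only.
- *That early leavers distort the adjusted model.* Those lost before week 36 normally also lack the week-48 P1NP, so the primary analysis lacks them too. The extra loss is mainly those who miss week 36 but attend week 48.

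**Conclusion.** The concern holds in a limited form. The one covariate named for the confounder-adjusted sensitivity analysis is an on-treatment measurement, and no pre-exposure value exists to replace it or check it. The analysis therefore cannot be read as the adjustment for confounding that 9.2 describes.

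The weight is low. The primary paired t-test and the matching are untouched. The 0 to 6 point range rests on assumed shifts and correlations; only the SD of 40% and the 20-point target come from the plan. A reader might infer a bias of at least a few points, but that requires ruling out a zero shift, and nothing in the documents does so. Nor do they show that anyone's diet changed.

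**What to change.** Take the same 3-day food recall at week 24, before the first vitamin D capsule, in cases and potential controls. Week 24 is already a scheduled visit and is already the starting point for the change in P1NP. The edits are:

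- **Main protocol 6.1:** place the recall in the column that holds week 24, and reword footnote 6 to limit it to week 24, since that column is shared with week 72.
- **Main protocol 6.3.16 and sub-study 6.0:** change the visit to week 24. Keep 6.3.16 worded for all participants, so that anyone later chosen as a control has a value.
- **Sub-study 9.2:** state that the regression uses week-24 intake. Label any week-36 recalls, whether already collected or kept as a repeat, as on-treatment intake. Report them descriptively or in a separate, declared co-intervention analysis, not as confounder adjustment.

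The cost is small: the same form at an existing visit, plus wording. If the recall is moved rather than repeated, on-treatment intake is no longer recorded. Subjects already past week 24 when the change takes effect will have no pre-exposure value. Sub-study 2.1 reports about one third of the planned 400 enrolled by April 2014, so many could still have supplied one when the sub-study was written.

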7.0 CLINICAL MANAGEMENT

Instructions are provided only for toxicities related to study therapy (vitamin D). The grading system for drug toxicities is located in the Division of AIDS Table for Grading the Severity of Adult and Pediatric Adverse Events, Version 1.0, December 2004 (Clarification dated August 2009), located at the Division of AIDS Regulatory Support Center Web Site: <http://RSC.tech-res.com/safetyandpharmacovigilance>.

For toxicities attributed to vitamin D, investigators may discontinue therapy.

7.1 Toxicity

The general guidelines presented below apply to toxicities that are not specifically addressed in section 7.2.

Grade 1 or 2

Subjects who develop a Grade 1 or 2 AE or toxicity may continue vitamin D without alteration of the dosage. For subjects experiencing Grade 1 or 2 AEs who choose to discontinue vitamin D, the site investigator should contact the protocol chair, and encourage the subject to complete other aspects of CCTG 595.

NOTE: If subjects discontinue study therapies due to experiencing Grade 1 or 2 AEs, this should be noted in the CRF as the reason for discontinuation.

Grade 3

If the investigator has evidence that the AE was NOT caused by vitamin D, dosing may continue. Subjects who develop a Grade 3 AE or toxicity thought to be related to vitamin D, should have vitamin D withheld. The subject should be reevaluated weekly until the AE returns to Grade ≤ 2 or baseline, at which time the study therapies may be reintroduced, at the discretion of the site investigator or according to standard practice.

If the same Grade 3 AE recurs within 4 weeks of restarting treatment, vitamin D must be permanently discontinued. However, if the same Grade 3 AE recurs after 4 weeks, the management scheme outlined above may be repeated.

Subjects experiencing a Grade 3 AE requiring permanent discontinuation of vitamin D should be followed weekly until resolution of the AE and should be encouraged to complete the follow-up protocol study evaluations.

Grade 4

Subjects who develop a Grade 4 symptomatic AE or toxicity will have vitamin D permanently discontinued. Subjects experiencing a Grade 4 AE requiring permanent discontinuation of vitamin D should be followed weekly until resolution of the AE and encouraged to complete the follow-up protocol study evaluations.

7.2 Specific Management

7.2.1 Kidney Stones

Subjects who develop signs and symptoms consistent with urinary tract obstruction should have further evaluation. Subjects with evidence of a new kidney stone on study will be taken off vitamin D but continue to be followed on study.

8.0 CRITERIA FOR DISCONTINUATION

8.1 Permanent Treatment Discontinuation

- Drug-related toxicity
- Requirement for prohibited concomitant medications
- Subject develops a kidney stone (see section 7.3.1).
- Completion of treatment as defined in the protocol.
- Request by subject to discontinue treatment.
- Discontinuation of PrEP for any reason
- Clinical reasons believed serious by the physician, even if not addressed in the toxicity section of the protocol.

9.0 STATISTICAL CONSIDERATIONS

9.1 Sample size justification

In ACTG 5280, administration of vitamin D-calcium resulted in a significant reduction in

the magnitude of the rise in BTMs P1NP and CTX ⁹. Because of more consistent association with changes in BMD with P1NP, this will be used as the primary surrogate marker to reflect bone health. Data on TDF effects on P1NP levels in the absence of HIV infection (e.g. during PrEP) are not available. In A5280, at week 24 P1NP increased by 60% with placebo and 36% with vitamin D-calcium ($p < 0.001$). If we anticipate that supplementation with vitamin D results in a decrease of similar magnitude from week 24 to week 48, then the expected intervention effect size is in the range of 24%. The SD of the change in P1NP at month 6 for the vitamin D-calcium group was 63%, but it is anticipated that the variability of P1NP levels in this study will be much less than that in HIV infected subjects undergoing a variety of pro- and anti-inflammatory changes after initiation of ART as in A5280. If we anticipate that in the absence of vitamin D supplementation that P1NP will increase by 20% and those receiving vitamin D will experience a reduction of this amount at week 48, then with an SD of the change in P1NP of 40%, a sample size of 44 cases and 44 controls will provide 80% power to detect a significant difference in the change in P1NP from week 24 to week 48 between cases and controls using a paired t-test with a two-sided $\alpha = 0.05$. In order to account for attrition, a sample size of 100 is proposed, consisting of 50 vitamin D treated cases and 50 matched controls.

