1.0 HYPOTHESIS AND STUDY OBJECTIVES

1.1 *Hypothesis*

Supplementation with vitamin D 4000 IU/day will significantly blunt the increases in BTMs that occur after initiation of PrEP with Truvada.

1.2 *Primary Objective*

To compare the change in P1NP levels from week 24 through week 48 among subjects (cases) who receive vitamin D 4000 IU/day to the change in levels seen in matched unsupplemented controls.

1.3 *Secondary Objectives*

1.3.1 To compare the change in CTX levels from week 24 through week 48 among subjects who receive vitamin D 4000 IU/day to the change in levels seen in matched unsupplemented controls.

1.3.2 To compare the change in PTH level from week 24 through week 48 among subjects who receive vitamin D 4000 IU/day to the change in levels seen in matched unsupplemented controls.

1.3.3 To compare vitamin D levels at week 48 among subjects who receive vitamin D 4000 IU/day and matched unsupplemented controls.

1.3.4 To demonstrate the change in P1NP, CTX, PTH, and vitamin D levels from baseline to week 24 in both cases and controls.

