In ACTG 5280, vitamin D-calcium supplementation prevented the increase in parathyroid hormone (PTH) and blunted the increase in bone turnover markers (BTMs), including P1NP (a marker of bone formation) and CTX (a marker of bone resorption). Importantly, there was a good correlation between changes in DXA-measured BMD over time and changes in BTMs, particularly with P1NP. The percentage change of P1NP at week 48 correlated with the percentage change in total hip BMD ($r = -0.32$, $p = 0.01$) as well as the change in lumbar spine BMD ($r = -0.37$, $p = 0.002$) [Overton ET, unpublished data]. Due to the difficulties and expense of performing DXA scans in a clinical trial, P1NP levels are proposed as the primary outcome measure for this pilot trial.

CCTG 595 is an open-label clinical trial of the effect of a text messaging intervention vs. standard of care on adherence to Truvada as PrEP in MSM at increased risk for HIV infection (ClinicalTrials.gov Identifier: NCT01761643). Approximately 1/3 of the planned 400 subjects have been enrolled as of April 2014. Study sites include University of California at San Diego, University of Southern California, and Harbor-UCLA Medical Center.

Rationale for use of vitamin D dose: The dose of vitamin D (4000 IU/day) in this protocol carries little risk for the study subjects. This dose was without adverse effects in a more ill population, namely the HIV-infected subjects in ACTG 5280 (see above). Generally, vitamin D supplementation is well tolerated and safe. Dosages up to 10,000 IU daily in healthy adults is considered safe and the current upper U.S. Dietary Reference Intake of 2,000 IU daily is considered to be well below the actual physiologic requirements^{10,11}. The Institutes of Medicine guideline considers 4000 IU/day to be the safe upper limits for daily intake for adults <http://www.iom.edu/Reports/2010/dietary-reference-intakes-for-calcium-and-vitamin-D/DRI-values.aspx>. Several studies have focused specifically on the safety of chronic daily administration of 4000 IU¹²⁻¹⁴. In these studies, 228 adult subjects received 4000 IU/day vitamin D with excellent tolerability, no toxicity, and a concomitant increase in 25 (OH) vitamin D levels ranging from 39-51 ng/mL. No abnormalities in serum calcium or urinary calcium excretion were noted.

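### Vitamin D sub-study: the 80% power stated for a 20% difference with 44 matched pairs does not follow from the printed inputs; 44 per group does follow from the 24% effect in the same section

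*Combined protocol and SAP*

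**What the plan says.** The sub-study's primary objective is a contrast of changes between groups: "To compare the change in P1NP levels from week 24 through week 48 among subjects (cases) who receive vitamin D 4000 IU/day", against the change in matched controls who are not supplemented. Sub-study section 9.2 names the test: "The primary endpoint analysis will use a paired t-test to compare the changes in P1NP levels from week 24 to 48 weeks". Controls "will be matched 1:1 by randomization arm in the CCTG 595 main study", and also by age, race/ethnicity, season of study entry and BMI.

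Sub-study section 9.1 builds the sample size in three steps:

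- From an earlier treatment trial (P1NP up 60% on placebo and 36% on vitamin D-calcium), it takes an expected effect of about 24%.
- It reports that trial's spread, "The SD of the change in P1NP at month 6 for the vitamin D-calcium group was 63" percent, and expects less variability in this population.
- It then opens a new assumption: a 20% rise without vitamin D and a reduction of that amount with it. It concludes that "with an SD of the change in P1NP of 40%, a sample size of 44 cases and 44 controls will provide 80% power".

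To allow for attrition, "a sample size of 100 is proposed, consisting of 50 vitamin D treated cases and 50 matched controls". The Analysis row of the synopsis repeats the claim: "A sample size of 44 subjects per group will provide 80% power to detect a 20% change in P1NP means". Neither place gives a within-pair correlation, or says whether the 40% is a per-person SD or the SD of the paired difference.

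**The concern.** The power of a paired t-test depends on the SD of the within-pair difference in change. Section 9.1 gives an SD of the change without saying whose change it is. The natural reading is per person, because the 40% takes the place of a one-group SD of 63%. To get from a per-person SD to the SD of the paired difference one needs the within-pair correlation, and the plan does not state it. The same section also prints two effect sizes, 24% and 20%, and does not say why the second replaces the first.

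What is at stake is how the sub-study's primary result will be read. A null P1NP finding means one thing if power for a 20% difference was 63% and another if it was 90%. From the text a reader cannot tell which applies.

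**Working it through.** **Inputs, from sub-study 9.1 and the synopsis.** Difference in change d = 20 percentage points (24 as the other printed effect); SD = 40; n = 44 pairs; two-sided alpha 0.05; paired t-test. The within-pair correlation ρ is not given, so I vary it from 0 to 0.5.

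**Formulas.** SD of the paired difference: SDd = 40·√(2(1 − ρ)) if 40 is per person, or SDd = 40 directly. Noncentrality: λ = d·√n / SDd. Power comes from the noncentral t distribution with n − 1 = 43 degrees of freedom, critical value 2.017.

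**Step 1: try to reproduce 80% at d = 20.**

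- SDd = 40: λ = 20 × 6.633 / 40 = 3.32, power 90.0%. For 80%, 34 pairs suffice; 44 is the smallest number that reaches 90%.
- Per-person SD 40, ρ = 0: SDd = 56.6, λ = 2.35, power 63.0%. For 80%, 65 pairs are needed.
- Solving for 80% at 44 pairs: SDd = 46.3, so ρ = 1 − 46.29²/3200 = 0.33. With ρ = 0 the same SDd needs a per-person SD of 46.29/√2 = 32.7, not 40.

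Other standard calculations at d = 20 do not give 80% either: two-sample t 64.0%, two-sample normal 65.0%, paired normal 91.3%. One-sided testing gives 74.6% or 94.7% paired and 75.2% two-sample.

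**Step 2: try the 24% effect printed in the same section.** Unpaired two-sample normal formula, per-person SD 40, 80% power:

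n per group = 2(1.960 + 0.842)² × 40² / 24² = 43.6, rounded up to 44.

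This reproduces both printed figures. At n = 44 and d = 24, power is 80.4% by the normal formula, 79.5% by the two-sample t-test, and 78.6% by the paired t-test at ρ = 0. The paired test reaches 80% at a correlation of about 0.04. The same unpaired formula with d = 20 gives 63 per group.

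**Step 3: power over the correlation, per-person SD 40, paired t-test.**

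| ρ | SDd | 44 pairs, d = 20 | 44 pairs, d = 24 | 50 pairs, d = 20 |
|---|---|---|---|---|
| 0 | 56.6 | 63% | 79% | 69% |
| 0.2 | 50.6 | 73% | 87% | 78% |
| 0.3 | 47.3 | 78% | 91% | 83% |
| 0.4 | 43.8 | 84% | 94% | 89% |
| 0.5 | 40.0 | 90% | 97% | 93% |

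If all 50 planned pairs were complete, 80% at d = 20 would still need ρ of about 0.23.

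**The case against.** **The stated 80% may be right.** On the per-person reading it holds at a correlation near 0.33, and matching on five factors makes some positive correlation plausible. This stands. A reader might infer that the 80% is plainly false; the documents do not support that. What they show is a power figure that cannot be recovered from the inputs printed for it.

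**A hidden correlation need not be the explanation.** This also stands. A reader might infer that 80% can only come from an unstated correlation of about 0.33, but the 24% effect with an unpaired formula gives 44 per group with no correlation at all. That does not clear the text. Both places that state the 80% tie it to 20%, and the planned test is paired. Nor is 24% proved to be the source: 44 is also the smallest number of pairs giving 90% power for 20% when the SD of the paired difference is 40, so a misprinted power is possible too.

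**The effect is ambiguous.** A reduction of that amount could mean a 20% fall set against a 20% rise, a 40-point difference. Power would then exceed 99%, so this does not yield 80% either, and the synopsis supports 20.

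**The low end is pessimistic.** The 63% assumes no benefit from matching and 44 complete pairs. At 24% with 50 complete pairs and no correlation, power is 84%. This is fair, but the six extra pairs are there for attrition, and the claim in the text is for 44 pairs at 20%.

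**It is a pilot.** The sub-study says so: "P1NP levels are proposed as the primary outcome measure for this pilot trial". A null result would be judged mainly from its confidence interval and observed SD. That limits the consequence, but the plan still makes a formal power claim twice for its primary endpoint.

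**Conclusion.** The point holds as an inconsistency between a stated power and its printed inputs. For a 20% case-control difference with 44 pairs, the printed 40% gives 63% to 90% power over correlations of 0 to 0.5 if it is a per-person SD, and 90% if it is the SD of the paired difference. The stated 80% needs a correlation of about 0.33 that appears nowhere. The likeliest source is a calculation for 24% reported as 20%, but this is inference from matching numbers.

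A reader might go further and conclude that the sub-study is too small. The documents do not support that: the correlation is unknown, the intended effect is unresolved, and on one reading of the SD the sample exceeds what 80% requires. The direction of any misstatement cannot be settled from the text.

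These results assume that the 40% planning SD is accepted as given, that the effect is a difference in percentage change, and that all 44 pairs are complete. The main trial is not affected.

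**What to change.** Keep the sample size and the paired t-test. In sub-study 9.1 and in the Analysis row of the synopsis:

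- Reconcile 20% with 24%, state which effect the 80% refers to, and say that it is the case-control difference in change.
- Say whether 40% is the per-person SD of change or the SD of the within-pair difference.
- If it is per person, state and justify the within-pair correlation, or show power over a range such as 0 to 0.5.
- Restate the power to match.

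Possible wording on the per-person reading: *With a per-person SD of change of 40% and no within-pair correlation, 44 complete pairs give 79% power for a 24% case-control difference in change and 63% for a 20% difference; at a correlation of 0.3 these are 91% and 78%.*

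If the 40% is the SD of the paired difference: *44 complete pairs give 90% power for a 20% case-control difference in change.*

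The cost is one or two sentences in 9.1 and one line in the synopsis, with no change to enrolment, test or data collection. The drawback is that, on the per-person reading, the stated power for 20% will fall unless a correlation of about 0.33 or more can be justified. That value should not be chosen afterwards to recover the 80%.
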